For subjects receiving ascending multiple doses of oral IP in Part C of the study, the following scheme should be applied to the occurrence of a significant change in blood pressure, heart rate, other vital sign, ECG, laboratory result or any other significant adverse event considered by the investigator to be clinically relevant and directly related to the PO administration of IP.

- During the observation period after administration of the oral IP, a persistent (lasting more than 2 assessment time-points) adverse event, change in baseline systolic or diastolic blood pressure  $\geq 15\%$  or a change in heart rate  $\geq 25\%$  deemed clinically significant by the investigator should prompt a possible change for the next oral IP administration.
- The decision to completely withhold IP, to resume IP or to resume with a reduced dose will be made with agreement of Amgen, the investigator and the subject.
- The dose reduction after a clinically significant event should follow the guidelines below:
  - If the subject does not tolerate the 10 mg dose, IP should be completely withheld.

- If the subject does not tolerate the 30 mg dose, IP should be reduced to 15 mg for the next administration. Upon occurrence of a novel event of intolerance with 15 mg, dosage will be reverted to 10 mg in the next IP administration and maintained at 10 mg until the end of the 21-day dosage period.
- If the subject does not tolerate the 100 mg dose, IP should be reduced to 75 mg for the next administration. Upon occurrence of a novel event of intolerance with 75 mg, dosage will be reverted to 50 mg in the next IP administration and maintained at 50 mg until the end of the 21-day dosage period.
- Patients will be observed for at least 6 hours after the first administration of a new dose.

For more details on the administration of oral or intravenous investigational product, refer to the Investigational Product Instruction Manual.

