### 6.5.1 Criteria for Permanent Discontinuation of Amgen Investigational Product and Other Protocol-required Therapies due to Potential Hepatotoxicity

Investigational product should be discontinued permanently and the subject should be followed according to the recommendations in [Appendix A](#) (Additional Safety Assessment Information) for possible drug-induced liver injury (DILI), if ALL of the criteria below are met:

- TBL > 2x upper limit of normal (ULN) or INR > 1.5
- AND increased AST or ALT from the relevant baseline value as specified below:

Baseline AST or ALT value	AST or ALT elevation
< ULN	> 3x ULN

- AND no other cause for the combination of the above laboratory abnormalities is immediately apparent; important alternative causes for elevated AST/ALT and/or TBL values include, but are not limited to:
  - Hepatobiliary tract disease
  - Viral hepatitis (eg, Hepatitis A/B/C/D/E, Epstein-Barr Virus, cytomegalovirus, Herpes Simplex Virus, Varicella, toxoplasmosis, and Parvovirus)
  - Right sided heart failure, hypotension or any cause of hypoxia to the liver causing ischemia.

Approved

- Exposure to hepatotoxic agents/drugs or hepatotoxins, including herbal and dietary supplements, plants and mushrooms
- Heritable disorders causing impaired glucuronidation (eg, Gilbert's Syndrome, Crigler-Najjar syndrome) and drugs that inhibit bilirubin glucuronidation (eg, indinavir, atazanavir)
- Alpha-one antitrypsin deficiency
- Alcoholic hepatitis
- Autoimmune hepatitis
- Wilson's disease and hemochromatosis
- Nonalcoholic Fatty Liver Disease including Steatohepatitis (NASH)
- Non-hepatic causes (eg, rhabdomyolysis, hemolysis)

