**Table 14. Schedule of Assessments for Patient Cohort Part C**

Activity Study Day	10 mg PO Treatment													
	-28 to -2 k	-1	1					2	3	4	5	6	7	
Study Time (Hours)			Pre-dose	0	1	2	4	6	24 G	48 G	72 G	96 G	120 G	144 G
General & Safety Assessments														
Informed Consent J	X													
Medical History	X													
Physical Examination	X	X							X					
Weight	X	X												
Height	X													
Vital Signs (BP E , HR, RR, TEMP) A	X	X	X		X	X		X	X	X	X	X	X	X
ECG B	X		X		X	X	X	X						
Concomitant Medications														
Adverse Events I														
Serious Adverse Events														
Laboratory Assessments														
Chemistry, Hematology, & Urinalysis	X	X							X					
Troponin I	X		X						X		X			
NT-proBNP	X													
FSH (postmenopausal females only) C	X													
Pregnancy C	X	X												
HIV, HepCAb, HBsAg, HBcAb	X													
Drug, Alcohol, & Cotinine Screen	X	X												
Echocardiographic Assessments														
M-mode, 2-D, Flow & Tissue Doppler	X		X					X			X			
Investigational Product AdministrationE														
IP Administration PO (10 mg, Days 1-7)				X					X	X	X	X	X	X
Pharmacokinetic/Biomarker Assessments														
AMG 986 Plasma PK Collection			X		X	X	X	X	X					
Plasma and Serum Biomarker Collection			X											
Cell Pellet Collection			X											

Approved

Footnotes defined on page 75

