**Table 14. Schedule of Assessments for Patient Cohort Part C**

Activity Study Day	30 mg PO									
	8				9	10	11	12	13	14
Study Time (Hours)	168 G (Predose)	170	172	174	192 G	216 G	240 G	264 G	288 G	312 G
General & Safety Assessments										
Informed Consent										
Medical History										
Physical Examination										
Weight										
Height										
Vital Signs (BP E , HR, RR, TEMP) A	X		X		X	X	X	X	X	X
ECG B		X		X						
Concomitant Medications										
Adverse Events I										
Serious Adverse Events										
Laboratory Assessments										
Chemistry, Hematology, & Urinalysis	X				X					
Troponin I	X									X
NT-proBNP										
FSH (postmenopausal females only) C										
Pregnancy C										
HIV, HepCAb, HBsAg, HBcAb										
Drug, Alcohol, & Cotinine Screen										
Echocardiographic Assessments										
M-mode, 2-D, Flow & Tissue Doppler	X			X			X			
Investigational Product Administration										
IP Administration PO (30 mg, Days 8-14) E	X				X	X	X	X	X	X
Pharmacokinetic/Biomarker Assessments										
AMG 986 Plasma PK Collection	X	X	X	X	X					
Plasma and Serum Biomarker Collection	X									
Cell Pellet Collection										

Approved

Footnotes defined on page 75

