**Table 14. Schedule of Assessments for Patient Cohort Part C**

Activity Study Day	100 mg											EOS 30
	15 Predose					16	17	18	19	20	21	
Study Time (Hours)	336 G	337	338	340	342	360 G	384 G	408 G	432 G	456 G	480 G	
General & Safety Assessments												
Informed Consent												
Medical History												
Physical Examination	X										X	X
Weight												
Height												
Vital Signs (BP E HR, RR, TEMP) A	X	X		X		X	X	X	X	X	X	X
ECG B	X	X	X		X							X
Concomitant Medications												
Adverse Events I												
Serious Adverse Events												
Laboratory Assessments												
Chemistry, Hematology, & Urinalysis	X					X					X	X
Troponin I												X
NT-proBNP												
FSH (postmenopausal females only) C												
Pregnancy C												X
HIV, HepCAb, HBsAg, HBcAb												
Drug, Alcohol, & Cotinine Screen												
Echocardiographic Assessments												
M-mode, 2-D, Flow & Tissue Doppler	X				X			X			X	X
Investigational Product Administration												
IP Administration PO (100 mg, Days 15-21) E	X					X	X	X	X	X	X	
Pharmacokinetic/Biomarker Assessments												
AMG 986 Plasma PK Collection	X	X	X	X	X	X					X	
Plasma and Serum Biomarker Collection	X										X	
Cell Pellet Collection												

Approved

Footnotes defined on page 75

- 
- A Vital signs will be performed pre-dose for each day and at time points in the SOA.
  - B ECGs will be performed on Day 1 pre-dose and may be repeated. . At screening a single ECG will be performed. At baseline, a single ECG will be performed. . At all other time points single ECGs will be performed in a standardized method, and prior to blood draws or other invasive procedures.
  - C Female subjects only.
  - D BP measurements will be obtained in a semi-Fowler position at pre-dose and at time points listed in the SOA.
  - E Once daily PO AMG 986/placebo administration for 7 consecutive days.
  - F This assessment will be performed only if deemed necessary by the investigator upon review of the prior assessment.
  - G Procedures to be completed prior to dosing: physical examination, vital signs, ECGs, laboratory assessments, echocardiographic assessments, pharmacokinetic assessments.

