#### **7.2.15 Clinical Chemistry**

Blood samples for clinical chemistry will be collected at the time points specified in the Schedule of Assessments ([Section 7.1](#)). Baseline assessments will be taken on Day-1.

All laboratory tests must be reviewed and signed by the principal investigator or qualified designee. Additional safety laboratory assessments may be performed for subject safety.

The tests listed in

[Table 16](#) will be conducted and analyzed by standard laboratory procedures.

Approved

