## 9.2.2 Adverse Events

### 9.2.2.1 Reporting Procedures for Adverse Events That do not Meet Serious Criteria

Adverse events possibly related to any study procedures/study-activity are reported from signing of the ICF. All other adverse events are reported from the time of randomization (first dose of investigational product). The investigator is responsible for ensuring that all adverse events observed by the investigator or reported by the subject that occur from signing of the ICF or from the time of randomization (after the first dose of IP) through the End of Study are reported using the Event CRF.

The investigator must assign the following adverse event attributes:

- Adverse event diagnosis or syndrome(s), if known (if not known, signs or symptoms),
- Dates of onset and resolution (if resolved),
- Severity [and/or toxicity per protocol],
- Assessment of relatedness to IP (AMG 986 or placebo),
- Assessments of relatedness to any study-mandated activity/procedure and
- Action taken

The adverse event grading scale used will be the Common Terminology Criteria for Adverse Events (CTCAE). The grading scale used in this study is described in [Appendix A](#).

The investigator must assess whether the adverse event is possibly related to the investigational product (AMG 986 or placebo). This relationship is indicated by a “yes” or “no” response to the question: Is there a reasonable possibility that the event may have been caused by the investigational product (AMG 986 or placebo)?

The investigator must assess whether the adverse event is possibly related to any study-mandated activity [eg, administration of investigational product, protocol-required therapies, use of medical device(s) and/or procedure (including any screening procedure(s))]. This relationship is indicated by a “yes” or “no” response to the question: “Is there a reasonable possibility that the event may have been caused by a study activity [eg, administration of investigational product, protocol-required therapies, use of medical device(s)], and/or procedure”?

The investigator is responsible for reviewing laboratory test results and determining whether an abnormal value in an individual study subject represents a clinically significant change from the subject’s baseline values. In general, abnormal laboratory findings without clinical significance (based on the Investigator’s judgment) are not to be

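### Part C: the only full laboratory panel drawn after repeated dosing at the level being left is taken on the step-up day, and nothing requires its result before the first 30 mg or 100 mg dose

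*Protocol*

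**What the plan says.** Protocol Section 3.1 and Table 6 give Part C as 10 mg daily on Days 1 to 7, 30 mg on Days 8 to 14 and 100 mg on Days 15 to 21. In Table 14 the on-treatment panel falls on Days 2, 8, 9, 15, 16 and 21. Footnote G, which applies to the 168 h and 336 h columns, reads: "Procedures to be completed prior to dosing: physical examination, vital signs, ECGs, laboratory assessments, echocardiographic assessments, pharmacokinetic assessments".

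Two other places deal with laboratory review. Section 7.2.15 states: "All laboratory tests must be reviewed and signed by the principal investigator or qualified designee". Section 9.2.2.1 adds: "The investigator is responsible for reviewing laboratory test results". Neither sets a time relative to the next dose.

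Laboratory values can change dosing. The Part C scheme in Section 6.2.1.3.3 is to be "applied to the occurrence of a significant change in blood pressure, heart rate, other vital sign, ECG, laboratory result" or another significant adverse event. When the liver criteria of Section 6.5.1 are met, "Investigational product should be discontinued permanently and the subject should be followed". Section 6.5.2 adds rules for withholding. All of these act on a value that is already known.

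Sections 3.1 and 6.2.1.3.1 place the Part C dose level review meeting (DLRM) at the end of dosing, so no committee review falls at either step.

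**The concern.** Escalation within a patient is a decision to give more drug, and the useful laboratory evidence is what followed repeated dosing at the current level. Here that evidence is collected just before the higher dose and may not be back in time. An abnormal transaminase, potassium or creatinine that developed over the week would then be seen only after the patient had taken about three times the previous dose.

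The Part C population gives this some weight. It admits eGFR down to 30 (60 in Parts A and B) and age up to 85 (55 in Parts A and B), on background heart failure drugs. The oral Part B schedule (Table 13) was denser: healthy subjects had panels on Days 2, 5 and 7 of their seven-day course. Part C patients have only Day 2 within Days 1 to 7.

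**Working it through.** The plan states no figure on this point, so there is none to reproduce. The check counts doses taken before each sample.

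**Inputs.** Panel times from Table 14: 24, 168, 192, 336, 360 and 480 h. Each is a pre-dose draw, so doses already taken = hours / 24, filled in as seven at 10 mg, then seven at 30 mg, then 100 mg.

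| Panel | Doses taken: 10 / 30 / 100 mg |
|---|---|
| Day 2 (24 h) | 1 / 0 / 0 |
| Day 8 (168 h) | 7 / 0 / 0 |
| Day 9 (192 h) | 7 / 1 / 0 |
| Day 15 (336 h) | 7 / 7 / 0 |
| Day 16 (360 h) | 7 / 7 / 1 |
| Day 21 (480 h) | 7 / 7 / 6 |

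**Age of the last earlier panel.** Before 30 mg: 168 - 24 = 144 h. Before 100 mg: 336 - 192 = 144 h. Each is 6 days and covers one of the seven doses at the outgoing level.

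**Troponin I.** This has its own row. Day 4 (72 h) follows three 10 mg doses, and Day 14 (312 h) follows six 30 mg doses.

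**Step size.** 30/10 = 3.0 and 100/30 = 3.33 in dose. Single-dose AUC in Table 3 rises 34100/12600 = 2.71-fold from 30 to 100 mg.

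**Doses ahead of the result.** Turnaround is an assumption. A result arriving at a dosing time is counted as arriving before that dose.

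| Turnaround | Higher doses before result, Day 8/15 draw | Same, Day 7/14 draw |
|---|---|---|
| Same day, before dosing | 0 | 0 |
| 24 h | 1 | 0 |
| 48 h | 2 | 1 |
| 72 h | 3 | 2 |

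Moving the draw alone closes the gap up to 24 h. Beyond that, only a requirement to have the result closes it.

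**Reading of footnote G.** The same list includes pharmacokinetic and echocardiographic assessments, and Section 7.2.14 sends echocardiograms to an outside vendor for analysis. Completed therefore most naturally means performed or collected. Where the protocol wants a result before dosing, it says so: a positive drug, alcohol or cotinine test on Day -1 bars dosing (Section 7.2.12).

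**Patients affected.** Planned active patients: 15 + 15 = 30. Section 2.4.1 reports eight already treated with AMG 986 at all three levels by 1 June 2018, before Amendment 8 of 27 July 2018. Remaining: 30 - 8 = 22, or 22 x 2 = 44 step-ups at most.

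**The case against.** The strongest reply is that the harm depends on something the documents do not show. With same-day results there is no lag, and collection details sit in manuals outside the protocol. That stands, and it is why the size is given as a range.

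There are also real safeguards:

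- Section 6.2.1.3.3 provides for at least 6 hours of observation after a new dose, and Table 14 schedules assessments 6 hours after dosing on Days 8 and 15.
- Section 7.2.15 allows extra safety laboratory tests, so an investigator may already draw on Day 7 or Day 14.
- Table 8 stops dosing for a single Grade 2 reaction or a suspected laboratory abnormality.
- Panels follow one day after each step.
- Healthy subjects took up to 650 mg daily for seven days. The 12 heart failure patients reviewed had only Grade 1 events, and Section 2.3 reports acceptable safety in renal impairment.

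These limit the consequence. None puts the result ahead of the dose: the extra tests are optional, Table 8 needs a known abnormality, and the Day 9 and Day 16 panels come after the first higher dose.

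A reader might infer that no chemistry at all is measured after repeated dosing before a step. Table 16 lists troponin I under chemistry, and the Day 4 and Day 14 draws contradict that reading.

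A reader might also take the synopsis sentence on DLRM review before a higher dose level either as closing the gap or as being breached. It covers only available data, and the Part C sections explicitly set that meeting at the end of dosing, so it does neither.

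**Conclusion.** The gap is real and modest. At both steps, the only full panel after more than one dose at the outgoing level is drawn on the day of the increase, and no text makes its review a condition of dosing. If the result is pending, the decision rests on a panel 6 days old that follows one dose at that level, supplemented by troponin.

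Under assumed turnaround from same day to 72 h, zero to three higher doses precede the result. The ceiling is 44 remaining active step-ups. The SAP records early discontinuation of the study, so the true number may be lower, and the correction now serves mainly the record and any reuse of the schedule.

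The documents do not support going further and saying that patients were put at demonstrated risk or that a signal was missed.

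**What to change.** In Table 14, move the pre-escalation panel from Days 8 and 15 to Days 7 and 14. Add a sentence requiring the investigator to review that result before the first 30 mg and first 100 mg dose. Where the laboratory reports the same day, keep Days 8 and 15 and require the result before dosing.

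No visit or sample is added, since patients already attend on Days 7 and 14 for dosing and vital signs. The earlier draw does have costs:

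- Each panel covers six rather than seven doses at the level.
- The immediate pre-step sample that pairs with Day 9 or Day 16 is lost.
- Day 7 becomes a fasting blood-draw day. Day 14 already has troponin.
- A site with turnaround beyond 24 h would have to delay the step.

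The same-day option avoids the first three and costs a short wait before that visit's dose.

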## **2.4 Risk/Benefit Assessment**

### **2.4.1 Risk Assessment**

AMG 986 has an identified risk of embryo-fetal toxicity and malformations. In developmental and reproductive toxicology studies in rats and rabbits, oral administration of AMG 986 resulted in abortions, embryo-fetal toxicity and external, visceral and skeletal malformations. Women of childbearing potential are not eligible to participate in this study, and male subjects must agree to practice an acceptable method of effective birth control and not donate sperm while on study and through 11 weeks after receiving the last dose of AMG 986. These inclusion/exclusion criteria will mitigate the risk of embryo-fetal toxicity.

AMG 986 has a potential risk of causing changes in blood pressure. Studies have shown that the principal effect of the apelin/APJ system is to counterbalance the renin-angiotension-aldosterone system, and apelin affects vascular tone and blood pressure. AMG 986-related cardiovascular changes in the nonclinical program were limited to modest and reversible decreases in mean blood pressure at the highest IV dose in the rat and small dose-independent increases in mean blood pressure in the anesthetized dog. Subjects will be closely monitored for changes in cardiovascular parameters, such as blood pressure, heart rate, and ECG measurements, and for signs and symptoms suggesting adverse events.

The nonclinical (toxicology and safety pharmacology) package suggests a safe profile for the initiation of clinical trials with AMG 986. Genetic toxicology and photosafety evaluations indicated that AMG 986 is not genotoxic or phototoxic. No AMG 986-related toxicity was identified in the rat or dog toxicology studies that were conducted with oral (6- and 9-months duration in rats and dogs, respectively) or IV (14-day studies) dose administration. The AUC-based exposure margins based on NO(A)EL doses from the rat and dog toxicology studies support the planned oral and IV infusion clinical dose ranges. Additionally, no AMG 986-related effects in the safety pharmacology studies were identified, including data indicating that QTc interval prolongation risk is low.

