- 109 Subject must be of age 18 to 85 years, have a diagnosis of HF confirmed by medical records for  $\geq 3$  months, and be in stable condition for at least 4 weeks.
- 110 Left ventricular ejection fraction (LVEF)  $\leq 40\%$  confirmed by echocardiogram, radionuclide ventriculography, cardiac magnetic resonance imaging, or contrast ventriculography within 12 months prior to randomization.
- 111 NYHA class II or III at screening
- 112 Sinus rhythm
- 113 NT-proBNP level  $\geq 250$  pg/ml
- 114 Patients will be treated with stable, optimal pharmacological therapy for a minimum of 4 weeks prior to randomization. Treatment of HFrEF includes at least beta-blockers (carvedilol, metoprolol succinate or bisoprolol) and a RAAS inhibitor (ACEi, ARB or sacubitril/valsartan).

Additional Inclusion Criteria for HFpEF patients

- 115 Subject must be of age of 18 to 85 years, have a diagnosis of HF confirmed by medical records for  $\geq 3$  months, and be in stable condition for at least 4 weeks.
- 116 Left ventricular ejection fraction (LVEF)  $\geq 50\%$  confirmed by echocardiogram, radionuclide ventriculography, cardiac magnetic resonance imaging, or contrast ventriculography within 12 months prior to randomization.
- 117 Left ventricular ejection fraction (LVEF) never  $\leq 40\%$  in the past
- 118 NYHA class II or III at screening
- 119 Sinus rhythm
- 120 NT-proBNP level  $\geq 250$  pg/ml

Approved

- 121 Patients will be treated with stable, optimal pharmacological therapy for a minimum of 4 weeks prior to randomization. Treatment of HFpEF includes at least a daily dose of diuretics equivalent to furosemide 40 mg.
- 122 For subjects in Parts A, B and C: Women must have negative results for both the screening (serum) and day -1 (serum or urine) pregnancy tests

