### **6.2 Investigational Product**

All investigational products will be administered at the research facility by a qualified staff member.

A physician or qualified designee must be available at the time of administration of investigational product.

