#### **6.2.1.1 Dosage, Administration, and Schedule**

In Parts A and B of the study, healthy subjects will receive investigational product (AMG 986 or placebo) in a fasted state. Subjects in the IV dose cohorts of Parts A and B will receive investigational product on an empty stomach (no food or liquids, except water, at least 2 hours prior to initial IV infusion) and refrain from food and liquid (except water) intake until after completion of the initial 1 hour infusion loading dose on study Day 1. Subjects in the PO dose cohorts of Parts A and B will receive investigational product on an empty stomach (no food or liquids, except water, at least 2 hours prior to drug administration) and refrain from food and liquid (except water) intake for at least 2 hours post dose.

In Part C of the study, subjects will receive oral investigational product administered on an empty stomach (no food or liquids, except water, at least 2 hours prior to drug administration) and refrain from food and liquid (except water) intake for at least 2 hours post dose.

Approved

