### 7.2.10 Vital Signs

Safety vital signs will be recorded by the investigator or designee at time points specified in [Section 7.1](#).

The following measurements must be performed: systolic/diastolic BP, HR, respiratory rate, and temperature.

Blood pressure will be measured in the following manner:

- Subjects should be lying in a semi-Fowler position quietly and comfortably for at least 5 minutes. The upper arm should be bare without constrictive clothing and supported at heart level.
- An appropriately sized cuff (cuff bladder encircling at least 80% of the arm) should be used to ensure accuracy. Neither the subject nor the observer (measurer) should talk during measurement.

In Parts A and B, BP measurements will be performed in a standardized method in triplicate approximately 2 minutes apart. Triplicate measurements of BP will be obtained at pre-dose and at time points corresponding to ECG monitoring. At time points in which ECG monitoring is not performed, single measures of BP will be obtained as part of the safety vital signs monitoring. In Part C, single BP measurements will be performed in a standardized method at pre-dose and at time points corresponding to ECG monitoring. At time points in which ECG monitoring is not performed, single measures of BP will be obtained as well. PK sample collection should occur after blood pressure measurements and ECG monitoring are completed.

Respiratory rate will be assessed by a full minute count. Abnormal measurements maybe repeated at the investigator's discretion. All data collected will be entered on the CRF.

The temperature location selected for a subject should be the same that is used throughout the study and documented on the vital signs CRF.

Record all measurements on the vital signs CRF. Abnormal measurements may be repeated at the discretion of the investigator and must be reported on the corresponding CRF page. When vital signs and blood sample collection occur at the same time, vital signs should be performed before blood samples.

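### Part C schedules post-dose blood pressure and heart rate only on the first day of each dose level (Days 1, 8 and 15); the other 18 of 21 dosing days have pre-dose readings only

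*Protocol*

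**What the plan says.** Protocol Table 14 (Section 7.1) gives Part C one column for each of Days 2-7, 9-14 and 16-21. Each of those columns carries footnote G: "Procedures to be completed prior to dosing: physical examination, vital signs, ECGs, laboratory assessments, echocardiographic assessments, pharmacokinetic assessments". Footnote A asks for vital signs before dosing each day and at the times in the table, so it adds no post-dose time.

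Section 7.2.10 adds blood pressure (BP) at ECG times: "In Part C, single BP measurements will be performed in a standardized method at pre-dose and at time points corresponding to ECG monitoring". After dosing, Part C ECGs are marked only on Days 1, 8 and 15.

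The Part C dose-reduction scheme in Section 6.2.1.3.3 begins: "During the observation period after administration of the oral IP, a persistent (lasting more than 2 assessment time-points) adverse event". It goes on to include a BP change of at least 15% or a heart-rate change of at least 25%. The only observation period that the section defines is this one: "Patients will be observed for at least 6 hours after the first administration of a new dose".

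Section 2.4.1 states: "AMG 986 has a potential risk of causing changes in blood pressure". Clinically significant vital-sign change is part of a primary endpoint (Section 10.1.1.1). SAP Section 10.5.3 summarises vital signs and their changes from baseline at each scheduled visit, by treatment group within each Part C cohort.

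**The concern.** Pre-dose readings are taken about 24 hours after the previous dose, when concentration is lowest. A BP or heart-rate effect that follows the peak could be missed on 18 of the 21 dosing days, including six of the seven at 100 mg.

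Part B does more in healthy subjects. On its last oral dosing day (Day 7, Table 13), vital signs are taken at 0.5, 1, 2, 3, 4, 6, 8 and 12 hours after the dose, at doses up to 650 mg. On the last dosing day of Part C (Day 21) there is one pre-dose reading. The protocol gives no reason for the difference. Inclusion criterion 114 requires HFrEF patients to be on a beta-blocker and a RAAS inhibitor, so the healthy-subject readings carry over only in part.

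At stake is a description of haemodynamic response after repeated doses at one level, in the patients for whom the drug is intended.

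**Working it through.** **1. Count of the schedule.** The plan states no figure for this, so I mapped the marks in the Table 14 vital-sign and ECG rows to their time columns.

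| Day | Dose | Vital signs, h post-dose | ECG, h post-dose | Times: vital-sign row | Times: with ECG-linked BP |
|---|---|---|---|---|---|
| 1 | 10 mg | 1, 2, 6 | 1, 2, 4, 6 | 3 | 4 |
| 8 | 30 mg | 4 | 2, 6 | 1 | 3 |
| 15 | 100 mg | 1, 4 | 1, 2, 6 | 2 | 4 |
| each other day | – | none | none | 0 | 0 |

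Days with pre-dose readings only: 6 + 6 + 6 = 18 of 21.

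**2. How close Day 15 is to steady state at 100 mg.** Let q be the share of a dose's total AUC that falls after 24 h. Day 15 then has (1 − q) from the 100 mg dose plus 0.3q left over from 30 mg dosing, so its ratio to steady state is 1 − 0.7q.

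- *Observed single-dose data (Table 3).* AUCinf/Cmax runs from 34100/5760 = 5.92 h (100 mg) to 169000/18400 = 9.18 h (650 mg). In a one-compartment model, half-life cannot exceed ln 2 times this ratio, which gives 4.1 to 6.4 h. With q = 2^(−24/half-life), the ratio is 0.988 to 0.948.
- *Predicted two-compartment data (Table 2).* For 100 mg, AUC24h is 24.7 µg·h/mL. With clearance 45 mL/h/kg and bioavailability 85%, total AUC is 85/(0.045 × kg), that is 31.5 at 60 kg and 27.0 at 70 kg (assumed weights). So 1 − q = 0.785 and 0.915, and the ratio is 0.849 and 0.941.

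The range is about 85-99%. CYP3A4 autoinduction is ignored.

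**3. What one added set would estimate.** Assume a per-reading systolic SD of 6 to 10 mm Hg, so that a change has SD × √2. The 95% half-widths are:

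- Within 15 treated patients, t(14) × SD × √2/√15: 4.7 (SD 6), 6.3 (SD 8), 7.8 (SD 10) mm Hg.
- Treated minus 5 placebo patients, t(18) × SD × √2 × √(1/15 + 1/5): 9.2 (SD 6), 12.3 (SD 8), 15.3 (SD 10) mm Hg. Part C placebo data are not pooled across cohorts (Section 10.1.3).

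**4. Chance threshold crossings with no drug effect.** I simulated 1,000,000 patients with assumed means of 125/75 mm Hg and 68 beats/min. Per-reading SDs ran from 6/4/4 to 10/7/7 (systolic, diastolic, heart rate), with a systolic-diastolic correlation of 0.5-0.7.

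- BP change of at least 15%: 6.5% to 36.7% of patients.
- BP, or heart-rate change of at least 25%: 6.9% to 42.4%, about 3 to 17 of 40.
- Confirmed in the same parameter by a second reading sharing 0-80% of its variance with the first: 1.4% to 30.9%, about 1 to 12 of 40.

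**The case against.** The strongest reply is that little is left to see. Day 15 readings are taken at 1, 2, 4 and 6 hours at nearly steady-state exposure, and Section 2.7 anticipates a rapid response. That stands, and it is why the point is a small one.

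Pre-dose readings may not be drug-free either. Under the predicted model with a 12 h half-life, concentration 24 h after one 100 mg dose is 0.39 µg/mL at 60 kg and 0.13 at 70 kg, or 0.52 and 0.18 at steady state. The 4.1 h half-life gives about 0.10. The dog-model target is 0.135 µg/mL. So the pre-dose readings have some value, although they are still far below peak.

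A reader might infer that Part C can show only pre-dose values after repeat dosing. The documents do not support that: Day 8 readings follow seven earlier daily doses and Day 15 readings follow 14. What is missing is narrower, namely post-dose values after the 2nd to 7th dose of the same level.

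A reader might also infer that the dose-reduction rule cannot operate. If the observation period is the 6 hours after the first administration of a new dose, the rule fits the schedule. It needs at least 3 time-points; BP has 4, 3 and 4, and Part C ECGs also record heart rate (Section 7.2.13).

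Other safeguards remain: adverse-event assessment, repeat measurements at the investigator's discretion, the Table 8 stopping rules, and the Part B data. Among the 12 heart failure patients reviewed (8 on AMG 986), Section 2.4.1 reports no serious adverse event and no discontinuation for an adverse event.

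Finally, the SAP records that the study ended early, so the reading may no longer be collectable. That limits what can be done now, but not the assessment of the protocol as written.

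**Conclusion.** The point holds in its narrow form. Part C has no scheduled post-dose BP or heart rate after the 2nd to 7th dose of any level. This rests on a direct count of Table 14 with its footnotes and Section 7.2.10, with no modelling.

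The consequence is modest. The gap concerns response to repeated doses at one level, not unseen exposure; that judgement depends on the 85-99% estimate, with its assumed body weights and no autoinduction. An added reading would give a descriptive within-group estimate and a safety check. It would not resolve a modest drug effect against placebo. The precision and chance-crossing figures depend on assumed variability, because the documents give none. This is a cheap improvement to consider, not an error in the plan.

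**What to change.** Add one BP and heart-rate set at 1 hour post-dose (409 h, without footnote G) to the existing Day 18 visit in Table 14, and summarise it by treatment group. The 1-hour time matches a Day 15 vital-sign time, and the Days 19-21 doses can still be changed. If BP has changed by at least 15% or heart rate by at least 25%, re-measure within minutes; only if that confirms it, repeat at 2 and 4 hours. No extra ECG is needed.

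The cost is one cuff-reading set and about one more hour on site per patient. No new visit, staff or invasive procedure is involved. Dosing is already on site: "All investigational products will be administered at the research facility by a qualified staff member". Patients must also already "refrain from food and liquid (except water) intake for at least 2 hours post dose", and Day 18 already includes an echocardiogram. The downside is that some patients will cross a threshold by chance, and those confirmed (about 1 to 12 of 40 under the assumptions above) would stay about 3 hours longer. The investigator's judgement of clinical significance still comes before any dose change.
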